Absorption of topiramate is rapid, with peak plasma concentrations occurring at approximately 2 hours following a 400 mg oral dose. The relative bioavailability of topiramate from the tablet formulation is about 80% compared to a solution. The bioavailability of topiramate is not affected by food.

The pharmacokinetics of topiramate are linear with dose proportional increases in plasma concentration over the dose range studied (200 to 800 mg/day). The mean plasma elimination half-life is 21 hours after single or multiple doses. Steady state is thus reached in about 4 days in patients with normal renal function. Topiramate is 15-41% bound to human plasma proteins over the blood concentration range of 0.5 -250 μ g/mL. The fraction bound decreased as blood concentration increased.

5.2.4 *Adverse Effects*

Topiramate at the dosage that will be prescribed in this proposal is well tolerated. The most common adverse events (AEs) that we observed in our alcohol treatment study were transient tingling, psychomotor slowing, weight loss, and dizziness. We acknowledge that other central nervous system adverse events have been reported by others, such as ataxia, speech disorders and related speech problems, cognitive slowing, mood disturbance, and nystagmus (eyes jumping), but these would appear to be more manifest at higher doses than what we have proposed. A rarer adverse event of topiramate is kidney stone, which was not seen in any of our previous studies. Topiramate has weak carbonic anhydrase properties. Thus, topiramate's concurrent use with other carbonic anhydrase inhibitors, such as acetazolamide and zonisamide, may increase the risk of kidney stone formation and should, therefore, be avoided. Topiramate may be associated with the development of metabolic acidosis.

Psychological risks can include distress and heightened sensitivity, which can occur as part of the behavioral treatments, clinical interviews, or completing self-reported ratings and questionnaires. While the possibility of such events is low, we will monitor these situations and provide an appropriate level of support. Such events will be documented fully in the case records.

5.2.5 *Withdrawal*

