10 SUBJECT SELECTION

10.1 Inclusion Criteria

- 1) Males and females who have given written informed consent
- 2) Subjects must be at least 18 years of age or older
- 3) Subjects must weigh at least 40 kg
- 4) Good physical health as determined by a physical examination, an electrocardiogram (ECG) within normal limits, and laboratory screening tests within acceptable parameters (see exclusion criteria below)
- 5) DSM-5 diagnosis of mild to severe alcohol use disorder
- 6) Record an expired CO level of ≥ 10 ppm or a urinary cotinine level of ≥ 3 at screening and prior to randomization
- 7) Smoking an average of ≥ 5 cigarettes/day in the 30 days prior to randomization
- 8) Currently drinking at least 8 standard drink units (SDUs) per week in the 30 days prior to randomization for women and at least 15 SDUs per week in the 30 days prior to randomization for men
- 9) Subjects must provide evidence of stable residence in the last month prior to enrollment in the study, and have no plans to move in the next 9 months. Stable residence is a domicile in which an individual can operate as if it were his or her own homestead and does not include shelters or halfway houses
- 10) The pregnancy test for females of child-bearing potential at screen and prior to randomization must be negative. Additionally, women of child-bearing potential must be using an acceptable form of contraception. These include, but are not limited to: oral contraceptives, hormonal (levonorgestrel) or surgical implants, or barrier plus spermicide
- 11) Literate in English and able to read, understand, and complete the rating scales and questionnaires accurately, follow instructions, and make use of the behavioral treatments
- 15) Willing to participate in a treatment program for nicotine and alcohol dependence

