A physical exam will be performed including the subject's weight. Vital signs will be taken, an ECG will be performed, and the subject will be queried on medication use in the 90 day period prior to signing consent. Subjects will be instructed that no new prescription/non-prescription medications are to be taken between the start of screening and randomization without informing the study staff. The subject's demographics will also be collected at this visit.

A urine drug test will be performed using a point of care test strip. Blood will be collected for hematology, chemistry and optional genotyping assessments. Urine will also be collected for urinalysis. Saliva will also be collected for cotinine level.

The MINI will be performed to assess diagnoses of psychiatric disorders in accordance with DSM-4 criteria. At screening the following questionnaires will be administered: Fagerström Test for Nicotine Dependence, AUDIT, CIWA-AR, Q-LES-Q, The Alcohol Craving Visual Analog Scales, The Nicotine Craving Visual Analog Scales, Wisconsin Smoking Withdrawal Scale, PANAS, CES-D, MOS-Sleep, Baseline Drug Use, and DrInC. Screening may be completed in a single visit or over two visits (e.g., a hematology or chemistry test needs to be repeated).

Subjects will be required to provide the name, phone number, and address of up to three contact persons who are likely to know their whereabouts.

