13.4 Intervention Phase

Subjects will be seen in person at the clinical site for 17 visits (screening, intervention phase and the one month follow-up visit) and will complete the three month follow-up visit over the phone. All subject clinic visits will be collected on source documents and entered into an electronic database, or entered directly into an electronic database and printed out and placed in the source documentation binder. Clinic visits should be scheduled on the same day of the week that the subject was randomized, if possible, but a 3-day window is allowed. In the event of a missed visit, subjects will have until the end of the same week to reschedule an appointment or if the subject is unable to visit the clinic then the visit may be conducted over the telephone.

If the subject comes to a visit outside the allowed window, assessments scheduled for this visit will be conducted and data will be recorded as if it were for that week's scheduled visit and recorded as an unscheduled visit. At each of the clinic visits during the intervention phase, subjects will receive a brief session with one or more study staff members who will systematically assess AEs since the last visit, take vital signs, measure weight, conduct a BBCET session, administer questionnaires, ask about concomitant medication use and contraceptive method, and assess drinking and smoking using the TLFB. A new supply of investigational product will be given and the medication bottle(s) from the previous period will be collected. Blood will be collected for chemistries and hematology and a physical exam and electrocardiogram will be performed at Week 19 (visit 15). Women of child bearing potential will have a repeat pregnancy test during Weeks 1, 4, 7, 10, 16 and 19. An alcohol breathalyzer will be administered at each visit to determine if the subject has a BAC ≤ 0.020 to complete the visit. A urine drug test will be performed intermittently throughout the study. If the subject misses a visit in which safety measures were collected, the safety measures should be collected at the next in-clinic visit.

The following assessments will be administered at each study visit during the intervention phase (Week 1, 2, 3, 4, 5, 6, 7, 8, 9, 10, 12, 14, 16, 18 and 19): Q-LES-Q, Alcohol Craving Visual

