13.6 Early Termination (ET)

If a subject wishes to withdraw from the study before completing all study visits during the treatment phase then the study staff will schedule an early termination visit. The early termination visit will include all procedures and assessments of visit number 15 (week 19).

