14.3 Blood Chemistry, Hematology and Urine

Blood chemistry and hematology will be performed to confirm the subjects' physical health. These tests will include: complete blood count (CBC), sodium, potassium, chloride, calcium, phosphorus, total protein, albumin, globulin, glucose, total bilirubin, alkaline phosphatase, albumin/globulin ratio, serum glutamic oxaloacetic transaminase (SGOT), serum glutamic pyruvic transaminase (SGPT), γ -glutamyl transferase (GGT), blood urea nitrogen (BUN), creatinine, uric acid, and lactate dehydrogenase.

Urine will be collected for routine urinalysis. Women of child-bearing potential will receive a urine pregnancy test as scheduled in Table 1. Additionally, women of child-bearing potential participating in this study will be required to use an acceptable form of contraception, which includes but is not limited to the oral contraceptive pill, barrier (diaphragm and condom) plus spermicide, or hormonal or surgical implants.

An onsite urine drug screen will be performed at the screening visit to clear each subject for randomization. This UDS must be negative for all drugs. If a patient tests positive for a drug, he or she will be permitted one repeat urine drug screen prior to randomization. At site PIs' discretion, should a patient test positive again during the repeat UDS, he or she may rescreen (including re-consenting) 30 days from the end of the original 14 day period for randomization, which began when the informed consent was signed at the first screen visit. Urine drug screens will be repeated intermittently throughout the study.

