Medical and scientific judgment should be exercised in deciding whether a case is serious in situations where important medical events may not be immediately life-threatening or result in death, hospitalization, disability or incapacity but may jeopardize the subject or may require medical intervention to prevent one or more outcomes listed in the definition of serious. These should usually be considered as serious.

Simply stopping the suspect drug does not mean that it is an important medical event; medical judgment must be used.

Examples of such events are:

- Angioedema not severe enough to require intubation but requiring intravenous hydrocortisone treatment.
- Hepatotoxicity caused by paracetamol (acetaminophen) overdose requiring treatment with N-acetylcysteine.
- Intensive treatment in an emergency room or at home for allergic bronchospasm.
- Blood dyscrasias (e.g., neutropenia or anemia requiring blood transfusion, etc.) or convulsions that do not result in hospitalization.
- Development of drug dependency or drug abuse.

E. SPECIFIC INSTRUCTIONS – LABORATORY/ECG ADVERSE EVENT

A laboratory or ECG AE is any clinically significant worsening in a test variable that occurs during the course of the study, whether or not considered to be investigational product related. For each such change, provide the information requested on date of test, severity, likelihood of a relationship to investigational product, change in investigational product dosage due to the AE, and treatment required.

All laboratory AEs should be specified as an increased or decreased test result (e.g. “increased glucose”, “decreased potassium”) or as a term that implies an abnormality (e.g., hypercalcemia, azotemia, hypokalemia, or bradycardia). Any abnormal laboratory value that is considered clinically significant will be recorded as such on the clinical laboratory form in the source document along with a comment providing justification for that determination.

F. SERIOUS ADVERSE EVENT AND UNEXPECTED ADVERSE EVENT REPORTING

24 hour Reporting Requirements

Serious and unexpected adverse experiences or death occurring during the course of a research project, regardless of cause, must be reported to the IRB immediately according to institutional guidelines (i.e., within 24 hours). In addition, all sites must report all SAEs to UVa within 24 hours. [name], of UVa, is the IND holder and therefore responsible for reporting all SAEs to the FDA.

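### The chemistry panel in section 14.3 does not require bicarbonate (total CO2), so metabolic acidosis, a topiramate risk the protocol itself names, has no direct scheduled measurement.

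*Combined protocol and SAP*

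**What the plan says.** Section 5.2.4 (Adverse Effects) states: "Topiramate may be associated with the development of metabolic acidosis". It also mentions topiramate's weak carbonic anhydrase activity and the risk of kidney stones.

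Section 14.3 gives the blood tests as a list. It opens "These tests will include: complete blood count (CBC), sodium, potassium, chloride, calcium, phosphorus, total protein, albumin, globulin, glucose" and closes with "blood urea nitrogen (BUN), creatinine, uric acid, and lactate dehydrogenase". Bilirubin, alkaline phosphatase, the albumin/globulin ratio, SGOT, SGPT and GGT lie between. The safety paragraph of section 5.2.7 describes the laboratory monitoring as hepatic function and hematology.

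Blood chemistry is scheduled twice. At screening, section 13.2 says: "Blood will be collected for hematology, chemistry and optional genotyping assessments". Section 13.4 places the second draw at week 19 (visit 15), and section 13.6 makes an early-termination visit carry the same procedures.

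Appendix I, section E, provides the route for an abnormal result: "A laboratory or ECG AE is any clinically significant worsening in a test variable that occurs during the course of the study". A value judged clinically significant is recorded with a justification. Section 13.10(h) requires such findings to be followed until they resolve satisfactorily.

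**The concern.** The protocol names three related hazards in section 5.2.4 and acts on two. Kidney stones are an exclusion (10.2, criterion 6), and carbonic anhydrase inhibitors are disallowed (Appendix III). For the third, metabolic acidosis, the analyte that would show it directly is absent from the list, while sodium, potassium and chloride are present.

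Adverse events are elicited by an open question about how the subject has been feeling (14.1), which cannot be relied on to find a fall in bicarbonate without symptoms. Such a fall could go unrecorded in either topiramate arm. The trial, which compares 125 and 250 mg/day with placebo, could then end with no required data on it. A subject who starts with a low value would also not be recognised as such before the first dose.

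**Working it through.** The plan gives no figure on this point to reproduce. The check is a reading of the text, with some arithmetic on timing and cost.

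**1. What the panel covers (14.3).** Blood count: 1. Chemistry entries: sodium, potassium, chloride, calcium, phosphorus, total protein, albumin, globulin, glucose, total bilirubin, alkaline phosphatase, albumin/globulin ratio, SGOT, SGPT, GGT, BUN, creatinine, uric acid, LDH = 19. Total 1 + 19 = 20. Entries that measure bicarbonate, total CO2 or pH: 0.

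**2. Whether another provision fills the gap.** No bicarbonate, blood gas or anion gap appears elsewhere; CO in this protocol is carbon monoxide. The anion gap (Na − Cl − HCO3) cannot be computed without bicarbonate. Urinalysis does not measure serum acid-base status. Chloride and potassium can raise suspicion but do not establish acidosis.

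**3. Draws at which bicarbonate is required.** Screening: no. Week 19 or early termination: no. That is 0 of 2. The second chemistry mark in Table 1 seems to have shifted column in the extracted text, so the timing here comes from sections 13.4 and 13.6.

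**4. Timing of the second draw.** First day of week w = 7(w − 1) + 1.
- Week 15: 7 × 14 + 1 = Day 99.
- Week 19: 7 × 18 + 1 = Day 127.
- Last dose: Day 126 (12.1).
- Primary window, weeks 15–18: Days 99–126.

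**5. Drug remaining at that draw.** The half-life is 21 h (5.2.3), and the fraction left is 2^(−hours/21).
- 24 h after the last dose: 2^(−24/21) = 0.453, about 45%.
- 96 h: 2^(−96/21) = 0.042, about 4%.

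The 96 h case assumes a visit at the late edge of the 3-day window (13.4), Day 127 + 3 = Day 130. The plan does not say in which direction the window runs. An early visit, or an early-termination visit, could fall closer to dosing. The documents do not say how fast bicarbonate recovers, so these fractions describe the drug and not the analyte.

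**6. Number of assays.** The abstract gives 588 intake sessions, 294 randomized and 30% dropout.
- Expected completers: 294 × 0.70 = 205.8, about 206.
- Screening plus completers: 588 + 206 = 794.
- Screening plus all randomized: 588 + 294 = 882.

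These are upper figures. Not every intake session need reach a blood draw, a missed visit may be held by telephone (13.4), and attendance at the early-termination visit is only requested (13.10(g)).

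**The case against.** The strongest reply is that the list is introduced as what the tests will include, which is not exhaustive. A site laboratory may report total CO2 as a matter of course. Chloride and potassium are on the list, and a clinically significant change in either is a laboratory adverse event with follow-up, which could lead to an acidosis work-up. A reader might infer from the missing analyte that the scheduled bloods cannot detect acidosis or cannot start that route. The documents do not support so strong a statement. They support only that bicarbonate is not required and acid-base status is not directly measured.

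A reader might also infer that, once the analyte is added, a clean set of week 19 values would rule out acidosis above some rate on 125 or 250 mg/day. It would not. The draw nominally follows the last dose, no case is defined, and subjects who reduce or stop drug may stay in the study (12.1, 12.2). The number of values per arm is also not assured.

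Nor would a low screening value exclude anyone by rule. Inclusion criterion 4 points to the exclusion criteria, whose numeric laboratory limits cover SGOT, SGPT, BUN and LDH only (criterion 16). It would inform investigator judgement under criterion 20.

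Finally, the documents give no rate or severity for acidosis, they describe the drug as well tolerated at this dosage, and several safeguards exist: renal exclusions, disallowed carbonic anhydrase inhibitors, and adverse event and vital-sign checks at clinic visits. All of this lowers the priority. None of it supplies the measurement.

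**Conclusion.** The point stands as a low-cost improvement to safety monitoring. Bicarbonate is required in 0 of 20 listed entries and at 0 of 2 scheduled draws, although the protocol names the risk it would measure. Adding it would give a pre-dose baseline, a comparison with placebo at the end of treatment or at early termination, and a direct entry into the existing laboratory adverse event route.

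The gain is limited. With about 45% of drug left at 24 h and about 4% at 96 h, and with some subjects on reduced doses or off drug, the second value may understate the change during treatment. It comes too late to guide dosing in those who complete. No event rate, standard deviation or precision is claimed, because the documents give no basis for one. The sample size, the primary analysis and the primary endpoints are not affected.

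The conclusion assumes that sites follow the panel as written and that the second draw is at week 19, as section 13.4 says.

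**What to change.** Add serum bicarbonate (total CO2) to the panel in section 14.3, measured in all three arms at the existing screening and week 19/early-termination draws. State that a clinically significant fall is a laboratory adverse event under Appendix I, section E, with the justification recorded as that section already requires, and is followed to resolution under section 13.10(h).

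To protect the blind, report the week 19/early-termination result only after that visit's timeline follow-back is complete, and only to the clinician who reviews safety laboratory results. That follow-back closes the primary window (Days 99–126), so a later result cannot influence the self-reported data for it. The screening draw precedes randomization and carries no such risk.

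The cost is one analyte on blood already drawn (at most about 794 to 882 assays), a protocol change submitted to the IRB, and a slight hint at allocation at week 19 or early termination. No visit or venipuncture is added. A draw during treatment that could change dosing would be a separate decision and would need a stated action threshold; it is not part of this correction.

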14.4 BBCET Session Compliance

The BBCET session checklist is an instrument for provider assessments of session activities that was developed by the BBCET provider in our ongoing clinical trials. The checklist contains key interventions specific to the treatment. The rationale for the use of a BBCET session checklist is to provide a reminder of the key elements of the intervention and to provide an estimate of the overall level of treatment-specific intervention to each of the subjects in the study.

14.5 Clinical Institute Withdrawal Assessment for Alcohol-revised (CIWA-AR)

The CIWA-AR, a reliable and well-validated 10-item scale, will be used weekly to assess the severity of alcohol withdrawal symptoms. The CIWA-AR has been used both in clinical and research applications and has demonstrated both reliability and validity.

14.6 Wisconsin Smoking Withdrawal Scale

This questionnaire will be used weekly to assess the severity of nicotine withdrawal symptoms. It is a 28-item scale divided into 7 subscales related to smoking cessation: sadness, sleep, hunger, craving, concentration, anxiety, and anger.

14.7 Positive Affect Negative Affect Schedule (PANAS)

The 20-item PANAS is a psychometric scale developed to measure the largely independent constructs of positive and negative effect, both as states and traits.[58] Subjects will be asked to describe different feelings and emotions during the past week.

14.8 The Center for Epidemiologic Studies Depression Scale (CES-D)

The CES-D[59] was developed to measure symptoms of depression in community populations. The scale has been used in many research studies as a screen for the presence of depressive illness. When the scale was developed items were selected to represent the major components of depression on the basis of the clinical literature and factor analytic studies. Components include the following: depressed mood, feelings of hopelessness, feelings of worthlessness, loss of appetite, poor concentration, and sleep disturbance.

The measurement of mood is particularly important to both alcohol and nicotine studies. With respect to alcohol, abrupt cessation of intake in dependent individuals can be associated with mood disturbance including depression, anxiety, confusion, and irritability. Likewise, abrupt smoking cessation among those dependent on nicotine can be associated with negative affect[60] including depression and anxiety. Furthermore, because the FDA has included the monitoring of depression and suicidality for all individuals receiving an anticonvulsant (including topiramate), we have included specific measurement of those parameters using the CES-D.

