2 STUDY SCHEMA

3 STUDY SCHEDULE

Randomization		Target Quit Date						
	Screen	Weeks 1 to 5 (-5 to -1 weeks to TQD)		Weeks 6 to 10 (0 to +4 weeks from TQD)	Weeks 10 to 18 (+4 to +12 weeks from TQD)	Week 19 (+13 weeks from TQD)	Follow-Up Visit 1 month	Follow-Up Phone Call 3 months
Assessments	X	Weekly	Week 6 visit=TQD (0)	Weekly	Biweekly	X	X	X
Psychosocial Intervention	—	Weekly		Weekly	Biweekly	X	—	—
Medication Dispensation	—	Weekly		Weekly	Biweekly	—	—	—

Table 1: Time and Events Schedule

Assessment		Investigational Product Administration																
Study Week	-4 to -1	1	2	3	4	5	6	7	8	9	10	12	14	16	18	19/ ET	F/U 1 month	F/U 3 month (phone)
Visit Number	S	1	2	3	4	5	6	7	8	9	10	11	12	13	14	15	16	17
Subject characteristics																		
Informed consent	x																	
Demographics	x																	
Alcohol Use Disorders Identification Test (AUDIT)	x																	
Fagerström Test for Nicotine Dependence	x															x	x	
Tobacco Use History Questionnaire	x																	
Baseline Drug Use	x																	
MINI for DSM-4, plus supplement	x																	
Efficacy																		
Timeline follow-back*	x	x	x	x	x	x	x	x	x	x	x	x	x	x	x	x	x	x
Carbon monoxide level	x	x	x	x	x	x	x	x	x	x	x	x	x	x	x	x	x	x
Urinary cotinine level****	x	x																
Quality of Life Enjoyment and Satisfaction Questionnaire (Q-LES-Q)	x	x	x	x	x	x	x	x	x	x	x	x	x	x	x	x	x	x
Alcohol Craving Visual Analog Scales	x	x	x	x	x	x	x	x	x	x	x	x	x	x	x	x	x	x
Nicotine Craving Visual Analog Scales	x	x	x	x	x	x	x	x	x	x	x	x	x	x	x	x	x	x
Salivary cotinine level	x															x		
Clinical Institute Withdrawal Assessment for Alcohol scale – Revised (CIWA-AR)	x	x	x	x	x	x	x	x	x	x	x	x	x	x	x	x	x	x
Wisconsin Smoking Withdrawal Scale	x	x	x	x	x	x	x	x	x	x	x	x	x	x	x	x	x	x
Positive Affect Negative Affect Schedule (PANAS)	x	x		x		x		x		x						x	x	
The Center for Epidemiologic Studies Depression Scale (CES-D)	x	x	x	x	x	x	x	x	x	x	x	x	x	x	x	x	x	x
Medical Outcomes Sleep Scale (MOS – Sleep)	x	x				x				x		x		x		x		
Drinker Inventory of Consequences (DrInC)	x	x			x		x		x	x	x	x	x	x	x	x		
Psychosocial intervention																		
Brief behavioral compliance enhancement treatment (BBCET)		x	x	x	x	x	x	x	x	x	x	x	x	x	x	x		

Assessment	Investigational Product Administration																	
	-2 to -1	1	2	3	4	5	6	7	8	9	10	12	14	16	18	19/ ET	F/U 1 month	F/U 3 month (phone)
Study Week																		
Visit Number	S	1	2	3	4	5	6	7	8	9	10	11	12	13	14	15	16	17
Subject characteristics																		

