10.2 Exclusion Criteria

- 1) Any current axis I DSM-4 psychiatric disorder (except for alcohol and nicotine addiction) that warrants treatment or would preclude safe participation in the protocol, including schizophrenia or other psychosis, bipolar disorder, major depression as assessed by the MINI, bulimia/anorexia nervosa, and dementia
- 2) Other neurological or psychiatric disorders, such as:
 1. Dependence on any substances except nicotine, alcohol and caffeine
- 3) Organic brain disease
 1. Risk of severe alcohol withdrawal as evidenced by history of alcohol withdrawal seizures, illusions/hallucinations, or delirium tremens.
- 4) Seizure disorders, epilepsy, severe head injury or coma
- 5) History of suicide attempts (5 years prior to screening) as assessed by the MINI and/or current suicidal ideation/plan as assessed by the MINI
- 6) Serious medical illnesses including but not limited to:
 1. Uncontrolled severe hypertension
 2. Kidney stones
 3. Significant unstable heart disease, including myocardial infarction
 4. Unstable angina
 5. Clinically significant cardiovascular abnormality (ECG)
 6. Disease of the gastrointestinal system, liver, or kidneys that could result in altered metabolism, excretion of the study agent or absorption
 7. History of major gastrointestinal tract surgery (e.g., gastrectomy, gastrostomy, bowel resections)
 8. Current or historical diagnosis of chronic disease of the gastrointestinal tract (e.g., ulcerative colitis, regional enteritis, or gastrointestinal bleeding)
 9. Serious, potentially life-threatening, or progressive medical illness other than addiction that may compromise subject safety or study conduct
- 7) Severe or life-threatening adverse reactions to medications (including topiramate) in the past or during this clinical trial
- 8) Currently on active treatment with topiramate
- 9) Receipt of a drug with known potential for toxicity to a major organ system within 30 days prior to study entry (e.g., isoniazid, methotrexate)

- 10) Female subjects who are pregnant, lactating, or not adhering to an acceptable form of contraception at any time during the study
- 11) Concomitant (within 2 weeks of randomization) pharmacotherapy with anticonvulsants, psychomotor stimulant-type medications, and specific anidepressants like Elavil, Endep, Wellbutrin, and MAOIs.

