14.1 AEs

AEs will be assessed starting after the subject takes the first dose of investigational product. AEs assessed in the clinic will use an opened ended question: "How have you been feeling since your last visit?" If an AE is reported that requires medical attention, it should be reported to the medical team for evaluation and follow-up.

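### Section 14.8 claims specific measurement of suicidality by the CES-D, but no CES-D component it lists is suicidality, and the MINI, the one instrument tied to it, is scheduled at screening only

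*Combined protocol and SAP*

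**What the plan says.** Section 14.8 gives two reasons for including the CES-D. The first is that stopping alcohol or nicotine can disturb mood. The second is regulatory: it says the FDA includes depression and suicidality in what is to be monitored with anticonvulsants, topiramate among them, and that for this reason "we have included specific measurement of those parameters using the CES-D". It describes the scale's content as "depressed mood, feelings of hopelessness, feelings of worthlessness, loss of appetite, poor concentration, and sleep disturbance".

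Suicidality appears in one other place. Exclusion criterion 5 in section 10.2 reads "History of suicide attempts (5 years prior to screening) as assessed by the MINI and/or current suicidal ideation/plan as assessed by the MINI". Table 1 lists that interview as "MINI for DSM-4, plus supplement" and marks it at screening and at no later visit. The CES-D, by contrast, is given at every intervention-phase visit (section 13.4). Adverse events are elicited in the clinic by one open question: "How have you been feeling since your last visit" (section 14.1).

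**The concern.** The plan names a risk of the drug class and tells its readers that a particular scale measures it. If the scale as described does not, an ethics committee, the DSMB or a later reader would believe that suicidality is checked directly at each treatment visit when nothing in the described schedule does so.

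The timing makes this matter. Criterion 5 removes people with current ideation or a recent attempt at entry, so what remains of interest is ideation that begins on treatment. An interview given only at screening cannot detect that. Participants are asked to stop both alcohol and smoking at the start of week 6, which section 14.8 itself links to depression and anxiety, and two of the three arms receive topiramate.

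**Working it through.** No alpha, power, rate or sample size enters this point, and the plan states no figure to reproduce. The check sets the sections side by side.

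1. **What is claimed.** In section 14.8 the parameters said to be measured are the two named in the preceding clause, depression and suicidality. No other pair fits the sentence.

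2. **What the scale is said to contain.** The list in section 14.8 has six components. Suicidal ideation, plan or behaviour accounts for 0 of the 6. Hopelessness and worthlessness are related symptoms, but they are not suicidality, and criterion 5 treats suicidality as something to be assessed in its own right.

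3. **Where suicidality is assessed explicitly.** It is assessed by the MINI under criterion 5. In Table 1 the MINI has one mark, at screening. Sections 13.4 (intervention phase) and 13.5 (follow-up) do not list it.

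4. **How many visits are affected.** Section 13.4 gives weeks 1 to 10 (10 visits), weeks 12, 14, 16 and 18 (4 visits) and week 19 (1 visit): 10 + 4 + 1 = 15. The MINI is scheduled at 0 of these 15. With 98 per arm (section 15.5), 3 × 98 = 294 participants are covered, of whom 2 × 98 = 196 are assigned to topiramate.

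5. **Whether another part of the plan fills the gap.**
   - The safety assessments listed in the abstract include neither the CES-D nor any suicidality measure.
   - Table 1 places the CES-D in its efficacy block. Sections 15.1 and 15.4 treat it as an exploratory outcome, with section 15.4 grouping it under negative affect.
   - Section 13.8 says that a CIWA-AR total of 10 or more, or a high single item, leads staff to speak to the participant. No score or item of the CES-D is given a comparable role.
   - The yearly DSMB report described in section 13.10 summarises serious and unexpected adverse events. Ideation that was never elicited would not reach it.

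6. **What routes remain on treatment.** These are the open adverse event question (14.1), enquiry about changes in health at in-clinic visits (13.8), serious adverse event reporting (13.10 and Appendix I) and the undertaking to act on clinical deterioration (13.11). Each could bring suicidality to light; none is described as asking about it.

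**The case against.** The strongest reply is that the component list is introduced as what the components include, so it need not be complete, and that the CES-D items are not reproduced. That stands. A reader might infer that the CES-D has no suicidality item at all, but the documents show only that no listed component is one. If such an item exists, naming it would answer most of the point.

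The second reply is that participants are far from unobserved. They complete the CES-D at all 15 visits, the Wisconsin scale with its sadness subscale and, at some visits, the PANAS; staff assess adverse events at each visit; and a 24-hour emergency number is provided. This also stands. It would be wrong to say that the open adverse event question is the only route left, or that suicidal events could not be reported by arm: those recorded as adverse events could be tabulated. What these routes lack is a direct question put to everyone, and that is what section 14.8 claims to provide.

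A reader might also infer that the plan promises to report suicidality by dose and breaks that promise. It does not. It promises measurement and says nothing about tabulating suicidality.

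Finally, part of Appendix I is absent from the text available and the BBCET manual is a separate document, so the finding covers the available text. The places where an instrument would be scheduled and described (Table 1, sections 13.4 and 13.5, and section 14) are present.

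**Conclusion.** The concern holds as a mismatch between a stated safety measurement and the design described. Section 14.8 claims specific measurement of suicidality, its own account of the CES-D does not support that, and the instrument that does address suicidality is not repeated after screening. Unvolunteered ideation arising on treatment may be missed, and a comparison across arms would rest on spontaneous reports rather than on the same question put to every participant.

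The size is one of coverage, not of consequence: no described suicidality item at any of 15 treatment-phase visits. Without an event rate, no number of missed cases can be given. The primary and secondary efficacy analyses are unaffected.

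The conclusion assumes that the listed components fairly represent the scale and that the unavailable material schedules no suicidality instrument. It should be corrected, and the correction is small.

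**What to change.** Reconcile section 14.8 with the content of the CES-D and with Table 1, in this order:

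- If a CES-D item measures suicidality, name it in section 14.8 and say that its responses will be tabulated by arm with the safety data.
- If there is none, add the suicidality questions already used at screening beside the CES-D at in-clinic visits, mark them in Table 1, and tabulate the answers by arm with the safety data. Criterion 5 combines a five-year history of attempts with current ideation or plan, so the period each repeated question refers to needs to be stated.
- If neither is done, remove the statement that suicidality is specifically measured.

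The cost of the second option is some added time per visit. The number of questions is not given; they are part of an interview that section 14.25 puts at 15 minutes in full, so the addition should be shorter than that. The sponsor would also have to state how a positive answer is handled; no clinical rule is proposed here. The first and third options need only a change of text and, for the first, one more safety table.
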